1.1. Synopsis

Protocol Title: A Safety, Tolerability and Pharmacokinetic Study of Single and Multiple Doses of LY3526318 in Healthy Participants

Short Title: A Safety, Tolerability, PK and Pilot Food Effect Study of LY3526318 in Healthy Participants

Rationale:

LY3526318 is a small molecule that inhibits transient receptor protein ankyrin-1 (TRPA1), a calcium-permeable nonselective cation channel. There is healthy participant experience and preclinical evidence for TRPA1 antagonism in the alleviation of chronic pain.

In the Phase 1 study, J2D-MC-CVAA (CVAA), LY3526318 was well-tolerated at all doses. Single doses up to 300 mg and multiple doses (MDs) of 100 mg daily for 14 days were administered. Plasma exposure increased with increasing doses of up to 100 mg but did not increase further at doses of 200 or 300 mg. The lowest animal-toxicology no-observed-adverse-effect level (NOAEL) is approximately 3-fold higher than the higher human exposures achieved in Study CVAA. There were no serious adverse events (SAEs) observed in Study CVAA.

There was a high degree of interindividual variability in LY3526318 pharmacokinetics (PK). When a meal was consumed near the time of dosing, LY3526318 maximum observed drug concentration (C_{max}) and area under the concentration versus time curve from time zero to 24 hours post dose (AUC_{0-24}) decreased by approximately 80% and 86%, respectively. These exposure limitations are likely due to a conversion from a more soluble to a less soluble crystal form of LY3526318 in the gastrointestinal (GI) tract prior to absorption. **CC1**

Study J2D-MC-CVAC (CVAC) will evaluate the PK parameters of the new LY3526318 formulation in healthy participants after oral administration and includes a single-ascending-dose (SAD) portion (fasted and fed) (Part A) and a 5-day MD portion (Part B). The initial single dose level is 100 mg, the dose that produced maximum exposure in Study CVAA ($56 \mu\text{g}\cdot\text{h}/\text{mL}$). Up to 2 additional single dose levels may be administered; these doses would be selected to maintain human exposure below the lowest animal-toxicology NOAEL ($154 \mu\text{g}\cdot\text{h}/\text{mL}$, established in a 1-month monkey study). Up to two of the single doses that were administered in a fasted state may also be administered in a fed state (a high-fat meal or a light breakfast), to determine if food affects LY3526318 PK when administered in the new formulation. Additionally, one of the single doses will be administered daily for 5 days to assess safety and exposure.

Objectives and Endpoints

Objective	Endpoints
Primary (Part A – SAD)	

 To determine the pharmacokinetics of LY3526318 after a single oral dose administration 	
 AUC C_{max}
Primary (Part B – MD)	

 To determine the pharmacokinetics of LY3526318 after multiple oral dose administrations 	
 AUC C_{max}
Secondary (Part A – SAD)	

 To estimate the safety and tolerability of LY3526318 after single (Part A) oral administration to healthy participants To evaluate the effect of a meal on the pharmacokinetics of LY3526318 in fed versus fasted conditions 	
 AEs SAEs C_{max} t_{max} AUC
Secondary (Part B – MD)	

 To estimate the safety and tolerability of LY3526318 after multiple oral administrations to healthy participants 	
 AEs SAEs

Abbreviations: AE = adverse event; AUC = area under the concentration versus time curve; C_{max} = maximum observed drug concentration; MD = multiple dose; SAD = single-ascending dose; SAE = serious adverse event; t_{max} = time to C_{max} .

Overall Design

Study CVAC is a Phase 1, randomized, double-blind, placebo-controlled, SAD (Part A) and MD (Part B) study of LY3526318 in healthy participants.

Disclosure Statement: This is a 2-part study with 2 arms (LY3526318:Placebo) that are participant and investigator blinded.

Number of Participants:

A maximum of 16 healthy male or female participants will be enrolled. Due to the relatively small size of the study, participants who discontinue may be replaced.

Intervention Groups and Duration:**Part A - SAD**

The SAD of LY3526318 or placebo will be administered, beginning at a dose of 100 mg, the dose level that produced the highest exposure in Study CVAA. A single cohort of 8 healthy participants will be randomized to a sequence in which LY3526318 or placebo will be administered in a 3:1 ratio. In each dosing period, different participants will receive placebo. In this adaptive dose study, subsequent dose levels will be selected based on safety and PK. Doses will be selected to maintain geometric mean AUC_{0-24} below the lowest NOAEL from animal-toxicology studies (154 $\mu\text{g}\cdot\text{h}/\text{mL}$).

Following a screening period of up to 28 days, eligible participants will be confined to the clinical research unit (CRU) from Day -1 until all study assessments are completed on Day 3.

Sentinel dosing is not planned as this is not the first clinical study for LY3526318. Dose escalations to subsequent cohorts may occur at approximately 2-week intervals after review of safety data and available PK data through 24 hours post dose from at least 4 participants on active drug from the prior period. Of the 4 treatment periods planned for Part A, up to 3 single dose levels will be assessed in a fasted state (fasting at least 8 hours prior to and at least 4 hours after dosing). Up to two of these dose levels that were assessed in a fasted state may also be assessed in a fed state (a high-fat meal or a light breakfast 30 minutes prior to dosing).

Participants will return to the CRU for a final follow-up visit approximately 10 days after the final study intervention administration.

Part B - MD

LY3526318 or placebo will be administered daily for up to 5 days at a dose level not to exceed the highest dose used in Part A. Part B will begin following a review of Part A safety and PK data. Participants will be confined to the CRU throughout this 5-day dosing period and for an additional 72 hours for PK sampling. Eight treatment-naïve participants will be randomized to receive LY3526318 or placebo in a 3:1 ratio. Part B will involve dosing in a fasted or fed state (e.g., standard meal or a light breakfast as described in site-specific manual) depending on the results from Part A. The dose regimen and fed/fasting will be selected with the intent not to exceed the AUC_{0-24} achieved in Part A.

Participants will return to the CRU for a final visit on Day 14.

Data Monitoring Committee: No

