2.1. Study Rationale

Study CVAC is designed to evaluate safety, tolerability, and PK of oral LY3526318 in healthy participants when LY3526318 is administered as a new formulation. In a prior Phase 1 study (CVAA), exposure did not increase beyond that observed at 100 mg, and the concomitant food administration reduced exposure compared to the fasted state.

In this limited SAD study, a crossover design was chosen to limit the variability of PK, especially for the comparison of PK after fed and fasted conditions. Given treatment-emergent adverse events (TEAEs) were mild in the previous SAD and MD (to 14 days) studies, participants should be able to safely tolerate a maximum of 4 single doses with 14 days of washout between dosing periods. Placebo doses are included to assess TEAEs and limit bias. Similarly, given that a Phase 1 study was previously conducted, sentinel dosing is not necessary. In addition, safety and PK will be assessed prior to each dose escalation to mitigate the possibility of more severe adverse events (AEs) and the PK exceeding the mean area under the concentration versus time curve (AUC) of the monkey NOAEL.

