2.3. Benefit/Risk Assessment

There is no benefit anticipated for healthy participants administered LY3526318.

The current study will be conducted in accordance with principles outlined in the “Guideline on Strategies to Identify and Mitigate Risks for First-in-Human and Early Clinical Trials with Investigational Medicinal Products” (EMA 2017). In Study CVAA, no clinically significant safety or tolerability concerns were identified at the highest single dose administered (300 mg) or the highest multiple dose administered (100 mg once daily for 14 days). Because of the male-only AE observed in rats (seminiferous tubule degeneration), dosing in CVAA was limited to 100 mg for males, with higher doses being administered to females only. This effect was not observed in 2 subsequent male rat studies and was not observed in a 1-month monkey toxicology study, so males will be enrolled in the current study. As described in Section 4.3, subsequent dose regimens will be selected to maintain exposure below the nonclinical NOAEL exposure.

In a biomarker study (Study CVAB), there was evidence of target engagement at 3 hours, but not 24 hours after a single dose of 100 mg. Regarding the current study that uses a new formulation of LY3526318, exposure following the proposed initial dose of 100 mg is projected to be similar to or slightly greater than the exposure achieved in the prior study.

The benefit-risk for the participants treated with LY3526318 remains unchanged in relation to the coronavirus disease 2019 (COVID-19) pandemic as currently based on the results from clinical and nonclinical data. There is no evidence that administration of LY3526318 will lead to suppression or modulation of the immune system. In addition, the mode of action does not appear to have a substantial effect on the respiratory or cardiovascular system critically affected by a severe acute respiratory syndrome coronavirus 2 (SARS-CoV-2) infection. As the participants to be included in this study are generally young to middle aged and healthy (without major comorbidities), the study population is not considered to be a high-risk population for serious COVID-19 disease. Only persons with a negative SARS-CoV-2 test at admission to the CRU will be allowed to participate in the study. In addition, all appropriate measures to prevent SARS-CoV-2 infection during the study will be taken as detailed in site standard operating procedures (SOPs).

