4.1. Overall Design

This is a Phase 1, SAD (Part A) and MD (Part B) study of LY3526318 in healthy participants. Both parts are randomized, double-blind, and placebo-controlled. A maximum of 16 participants (SAD and MD cohorts of size 8, randomized 3:1) will be randomly assigned to study intervention such that approximately 16 evaluable participants complete the study.

Part A (SAD):

Single-ascending doses of LY3526318 or placebo will be administered under fasted conditions, beginning with a dose of 100 mg in a cohort of 8 participants. Up to 3 dose levels in a cohort of participants will be administered in a fasted state (fasted for at least 8 hours prior to dosing and for at least 4 hours after dosing). The dose escalation may be stopped if a projected dose may exceed the toxicology NOAEL. Each dose will be separated by at least 1 week. The initial single dose level is the equivalent of 100-mg original formulation, the dose that produced maximum $AUC_{0-\infty}$ ($56 \mu\text{g}\cdot\text{h}/\text{mL}$) in Study CVAA. This dose level was selected because it produced the highest exposure when administered using the original formulation of LY3526318, and if the new formulation produces the maximum theoretical exposure increase of 2-fold compared to the prior study, a 2-fold exposure increase is considered safe and appropriate. Up to 2 additional single dose levels may be administered in a fasted state and these doses would be selected to maintain human $AUC_{0-\infty}$ below the lowest animal-toxicology NOAEL ($154 \mu\text{g}\cdot\text{h}/\text{mL}$, established in a 1-month monkey study).

Doses that were administered in a fasted state may also be administered in a fed state to determine if food decreases exposure when LY3526318 is administered in the new formulation. For the fed state, a standardized, high-fat meal or a light breakfast (as described in site-specific manual) will be consumed prior to dosing. Approximately 50% of the total caloric content of the high-fat meal should be from fat. Study participants should eat this meal in 30 minutes or less, and the study intervention should be administered 30 minutes after the start of the meal. In all cases, study intervention should be taken with 1 glass (approximately 240 mL) of water, and no food should be allowed for at least 4 hours post dose. Water can be allowed as desired except for 1 hour before and after drug administration.

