4.3. Justification for Dose

In a prior Phase 1 study (CVAA), there were no clinically significant adverse events at the highest doses administered: 300 mg in the SAD and 100 mg/day for 14 days in the MD. These doses were administered to females only, but there was no apparent difference in exposure or tolerability at lower doses administered to males and females. 100 mg/day was selected as the highest dose for the MD, because plasma exposure did not increase with increasing dose beyond 100 mg. In addition, when a meal was consumed 30 minutes prior to a 100 mg dose, exposure was approximately 11% of that observed when participants fasted. The new formulation being administered in the current study was developed to increase absorption and to decrease the impact of food. The current formulation could produce exposures up to 2.5 times those of the prior form for any given dose level.

The NOAEL from Good Laboratory Practice toxicology studies was established in a 1-month monkey study (Study 00926044). There were no adverse effects in monkeys administered 1000 mg/kg/day, and the mean AUC₀₋₂₄ was 154 $\mu\text{g}\cdot\text{h}/\text{mL}$. As summarized in Table 4.1, in the clinical study, CVAA, a dose of 100 mg resulted in a mean AUC_{0-inf} of 56 $\mu\text{g}\cdot\text{h}/\text{mL}$, and this is planned to be the starting dose in CVAC. The planned maximum dose of 275 mg is based on an assumption of a dose-proportional increase in exposure. The determinant of the maximum dose will be the NOAEL AUC of 154 $\mu\text{g}\cdot\text{h}/\text{mL}$. In the event that a less-than-dose-proportional increase in exposure is observed, a unit dose higher than 275 mg may be used, as long as a mean AUC of 154 $\mu\text{g}\cdot\text{h}/\text{mL}$ is not exceeded. As a practical limit, the unit dose will not be more than 1000 mg. In addition, if a dose lower than 100 mg is needed to maintain AUC < 154 $\mu\text{g}\cdot\text{h}/\text{mL}$, de-escalation is permitted. For the multiple-dose portion of the study, the dose regimen and fed/fasting will be selected with the intent not to exceed the AUC₀₋₂₄ achieved in Part A.

Table 4.1. Margin of Safety for Oral Administration of LY3526318 Based on Administered Dose and Exposure

	Dose (mg/kg)	Dose (mg/m ²)	Dose Multiple ^a	AUC ($\mu\text{g}\cdot\text{h}/\text{mL}$) ^a	Exposure Multiple ^b
Human					
Starting dose (100 mg)	1.67	61.7		56	
Maximum dose (275 mg) ^c	4.6	170		154	
Rat NOAEL^d					

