Male	1000	6000	97 ^e 35 ^f	131	2.3 ^e 0.85 ^f
Female	1000	6000	97 ^e 35 ^f	295	5.3 ^e 1.9 ^f
Monkey NOAEL^g	1000	12000	194 ^e 71 ^f	154	2.8 ^e 1 ^f

Abbreviations: AUC = area under the concentration versus time curve; AUC_{0-inf} = area under the concentration versus time curve from time zero to infinity; AUC_τ = area under the concentration versus time curve during a dosing interval; NOAEL = no-observed-adverse-effect level.

- ^a AUC for humans is AUC_{0-inf} after a single dose. AUC for rat and monkey is AUC_τ after multiple doses.
- ^b Dose multiple is the dose in animals/dose in humans based on mg/m². Exposure multiple is the calculated AUC in animals/observed or predicted AUC in humans.
- ^c The planned maximum dose of 275 mg is based on an assumption of dose-proportional increase in exposure. The determinant of the maximum dose will be the NOAEL AUC of 154 $\mu\text{g}\cdot\text{h}/\text{mL}$. In the event that a less-than-dose-proportional increase in exposure is observed, a unit dose higher than 275 mg may be used, as long as a mean AUC of 154 $\mu\text{g}\cdot\text{h}/\text{mL}$ is never exceeded. As a practical limit, the unit dose will not be more than 1000 mg.
- ^d NOAELs from the 4-week, repeat-dose toxicity study (Study # 00926043).
- ^e Based on human exposure at 100 mg using the prior formulation (Study CVAA).
- ^f Based on the highest projected exposure (NOAEL of 154 $\mu\text{g}\cdot\text{h}/\text{mL}$) at a 275 mg dose using the new formulation.
- ^g NOAEL from the 4-week, repeat-dose toxicity study (Study # 00926044; no LY3526318-related effects were noted).

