6.0 Study Design

This is a Phase 1, randomized, double-blind and placebo-controlled single ascending dose (SAD, Part A) and multiple dose (MD, Part B) study of LY3526318 in healthy participants. A maximum of 16 participants (SAD and MD cohorts, size of 8) will be enrolled.

Part A (SAD):

A single cohort of 8 healthy participants will be randomized to a sequence in which LY3526318 or placebo will be administered in a 3:1 ratio. In each dosing period, different participants will receive placebo. In this adaptive dose study, subsequent dose levels will be selected based on safety and PK. Doses will be selected to maintain geometric mean $AUC_{0-\infty}$ below the lowest no-observed-adverse-effect level (NOAEL) from animal toxicology studies (154 μ g.h/mL).

Of the 4 treatment periods planned for Part A, up to 3 single dose levels will be assessed in a fasted state (fasting at least 8 hours prior to and at least 4 hours after dosing). Up to two of these dose levels that were assessed in a fasted state may also be assessed in a fed state (a high-fat meal or a light breakfast 30 minutes prior to dosing).

Randomized to Treatment/Sequence:

Treatment	SAD Periods [N=8]				
	Sequence [n]	A1 (f asted)	A2 (f asted)	A3 (f ed)	A4 (f ed)
1 [2]		P	L2	L3	L4
2 [2]		L1	P	L3	L4
3 [2]		L1	L2	P	L4
4 [2]		L1	L2	L3	P

Single doses are L1, L2, L3, L4, P (Placebo); L = level of dose (mg);

Abbreviations: N = number of participants; n = number of participants in specific population; SAD = single ascending dose.

Following a screening period of up to 28 days, eligible participants will be confined to the clinical research unit (CRU) from Day -1 until all study assessments are completed on Day 3. All participants will return to the CRU after the last study period for a final visit on Day 10.

Part B (MD):

After a dose is identified from Part A, multiple doses of LY3526318 or placebo will be administered for up to 5 days. Eight treatment-naïve participants will be randomized to receive LY3526318 or placebo in a 3:1 ratio. Additional participants will be enrolled for a total cohort size of 8 completers. Part B will involve dosing in a f asted or f ed state (e.g., standard meal or a light breakfast as described in site-specific manual) depending on the results from Part A. The dose regimen and fed/fasting will be selected with the intent not to exceed the AUC₀₋₂₄ achieved in Part A. Part B is not designed to assess the impact of food on exposure.

Randomized to Treatment/Sequence:

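### The 154 µg·h/mL exposure limit is described as the lowest animal NOAEL, but Table 4.1 lists 131 for male rats

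*Protocol*

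**What the plan says.** Four places describe the Part A limit as the lowest animal NOAEL and give it as 154 µg·h/mL:

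- Protocol 1.1, paragraph introducing Study CVAC: "these doses would be selected to maintain human exposure below the lowest animal-toxicology NOAEL". The same sentence attributes 154 to a one-month monkey study.
- Protocol 1.1, Part A: geometric mean AUC0-24 is to stay "below the lowest NOAEL from animal-toxicology studies". No species is named.
- Protocol 4.1: AUC0-inf is to stay "below the lowest animal-toxicology NOAEL", again attributed to the monkey study.
- SAP 6.0: geometric mean AUC0-inf is to stay "below the lowest no-observed-adverse-effect level (NOAEL) from animal toxicology studies". No species is named.

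The synopsis rationale adds that the lowest animal NOAEL is about 3-fold above the higher exposures seen in Study CVAA.

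Other sections treat 154 as the monkey value without calling it the lowest. Section 2.1 speaks of "the PK exceeding the mean area under the concentration versus time curve (AUC) of the monkey NOAEL". Section 4.3 derives 154 from the monkey study and says: "The determinant of the maximum dose will be the NOAEL AUC of 154".

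Table 4.1 lists three NOAEL exposures: male rat 131, female rat 295 and monkey 154. At the 154 limit it prints exposure multiples of 0.85, 1.9 and 1. Its footnote a states the basis: "AUC for rat and monkey is AUC_τ after multiple doses".

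**The concern.** An exposure multiple below 1 means that the permitted human exposure is above that animal NOAEL. The statement that exposure stays below the lowest NOAEL and the printed 0.85 cannot both be right.

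The statement describes a safety property of the threshold that caps dosing. Someone relying on the synopsis or SAP would conclude that the margin to every animal NOAEL is at least 1 anywhere under the limit. For male rats it is not, and men are enrolled. Section 2.3 explains their enrolment by saying of the male-only rat finding: "This effect was not observed in 2 subsequent male rat studies", and that it was also absent in monkeys. It does not say why exposure may go above the male-rat NOAEL. Sections 6.1 and 6.6.1 refer only to the NOAEL, without species or number, so the synopsis wording colours how they are read.

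**Working it through.** **Inputs.** From Table 4.1: NOAEL AUCs of 131 (male rat), 295 (female rat) and 154 (monkey), all in µg·h/mL. From Section 4.3: human AUC0-inf of 56 at 100 mg of the prior formulation. Section 4.1 describes 56 as the maximum in Study CVAA.

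**1. Reproduce Table 4.1.** Exposure multiple = animal AUC / human AUC (footnote b).

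| | At 56 | Printed | At 154 | Printed |
|---|---|---|---|---|
| Male rat | 131/56 = 2.34 | 2.3 | 131/154 = 0.851 | 0.85 |
| Female rat | 295/56 = 5.27 | 5.3 | 295/154 = 1.92 | 1.9 |
| Monkey | 154/56 = 2.75 | 2.8 | 154/154 = 1 | 1 |

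The planned maximum dose also reproduces: 100 × 154/56 = 275 mg. The table is sound, so 131 is not a misprint.

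**2. Is 154 the lowest on any tabulated scale?**

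- AUC: 131 < 154. Footnote a puts rat and monkey on the same basis, so this is like for like.
- mg/m²: rat 6000, monkey 12000.
- mg/kg: both 1000.

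No scale that separates the species makes the monkey lowest. Pooling the rat sexes would (arithmetic mean (131 + 295)/2 = 213; geometric mean √(131 × 295) = 197), but neither document states that convention and the table lists the sexes separately.

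**3. Size of the discrepancy.** 154 − 131 = 23 µg·h/mL; 154/131 = 1.176, or 17.6% above the male-rat value. In the other direction, 23/154 = 14.9%, the amount by which the limit would fall if set at 131.

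**4. The synopsis margin.** Taking 56 as the higher CVAA exposure, the lowest listed NOAEL is 2.34-fold above it and the monkey value 2.75-fold. The figure of about 3-fold fits the monkey.

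**5. Could exposure fall between 131 and 154?** The documents give no exposures from this trial, so these are assumptions with a range. Section 4.1 allows a formulation gain of up to 2-fold, and Section 4.3 up to 2.5-fold.

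- 100 mg: 56 with no gain, 56 × 2 = 112, 56 × 2.5 = 140.
- 250 mg (SAP 9.2.2): 56 if exposure plateaus as in CVAA with no gain; 56 × 2.5 = 140 if dose-proportional with no gain; 140 × 2.5 = 350 if dose-proportional with a 2.5-fold gain.

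A value of 140 lies between the two NOAELs: 140/131 = 1.07 and 140/154 = 0.91. The dose that reaches each value moves with the gain (none, 2-fold, 2.5-fold): 275, 137.5 or 110 mg for 154; 234, 117 or 94 mg for 131. No fixed mg figure represents either limit.

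**The case against.** The best case for the plan is that this is a disclosed labelling slip. The number is 154 wherever a limit is given. The synopsis and Section 4.1 name the monkey study in the same sentence as the word in dispute. The sponsor calculated and printed the 0.85. The SAP occurrence is design background on which no analysis depends. Section 2.3 addresses the male-rat finding and the protocol refers to the Investigator's Brochure for more, which is not among the documents. Dose decisions rest on observed PK and safety review, with stopping rules in Section 6.6.1.

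Most of that stands. The limit is neither hidden nor ambiguous, and nobody following the number 154 would dose differently because of one adjective. What does not stand is the claim itself: nothing in either document withdraws 131 or explains why 154 should count as lowest. Section 4.3 ties the GLP toxicology NOAEL to the monkey study, but neither document says that the rat study was non-GLP or was set aside.

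Footnote a might also be raised, since the human AUC is single-dose and the animal AUCs are multiple-dose. That affects the animal-to-human comparison, and under linear PK the two quantities are equal. It does not affect the ranking of rat and monkey.

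Two stronger readings are tempting. A reader might infer that 250 mg takes mean exposure above the male-rat NOAEL. The documents do not support this: the projections run from 56 to 350 and no observed exposure is given. A reader might also infer that exceeding 131 means harm. A NOAEL is an exposure without adverse effects, so passing it removes the margin over male rats but does not show toxicity.

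**Conclusion.** Wrong as written. The dose-limiting threshold is said to lie below every animal NOAEL, and by the protocol's own table it does not. The permitted mean exposure is up to 17.6% (23 µg·h/mL) above the male-rat NOAEL, with men enrolled. The margin to the lowest NOAEL at the CVAA exposure is about 2.3-fold, not about 3-fold.

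These figures rest only on Table 4.1 and the CVAA value of 56. The statement about the 131 to 154 range in practice depends on the assumed formulation gain and dose proportionality: the range is reachable on the protocol's own assumptions but not shown to be reached. Whether 154 is an acceptable limit for men is a toxicology judgement that the documents leave unargued. This point does not say that it is unacceptable.

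**What to change.** Wording change, preferred:

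- In the synopsis (margin sentence, Study CVAC paragraph and Part A), Section 4.1 and SAP 6.0, replace the description of 154 as the lowest NOAEL with the monkey NOAEL.
- Beside it, give the male-rat value: 131 µg·h/mL, with a multiple of 0.85 at the limit and 2.3 at the CVAA exposure. In the margin sentence, attribute the larger figure (2.75-fold) to the monkey.
- Add a sentence, for example in Section 4.3, saying why 154 rather than 131 is acceptable for enrolled men.

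The cost is a less favourable stated margin. No participant, sample or dose changes.

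If the sponsor cannot justify 154 for men, it should lower the limit to 131 in the protocol and SAP. That is a substantive change to dose selection: the limit falls by 14.9%, and 250 mg would be usable only if observed PK supports a mean AUC below 131. Either way, observed exposure rather than a fixed dose such as 234 or 275 mg should govern.

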6.6. Dose Modification

6.6.1. Dose Escalation

The decision to proceed to the next dose level (either an increase or a decrease) will be made by the study team and the investigator based on safety, tolerability, and preliminary PK data obtained at the prior dose level.

By nature of being a dose escalation study, data will be evaluated on an ongoing basis until the mean LY3526318 exposure is projected to reach the NOAEL.

No dose decision can occur without prior discussion and agreement between the investigator and the sponsor's medical monitor.

In the SAD, the decision to escalate to the next dose will be based on vital signs, AEs, ECGs, and clinical laboratory assessments from predose to Day 4 from at least 4 individuals randomized to LY3526318. Pharmacokinetics data through at least 24 hours after the current dose will be used to inform the dose escalation decision.

Safety data, AEs, SAEs, and adverse laboratory abnormalities will be independently assessed by the investigator and will be considered related to the investigational product unless there is clear evidence that the event is not related.

After review of these data, the investigator and sponsor will make an agreement on the appropriate dose for the next cohort/dose level. The magnitude of dose escalations may be reduced following data review, but subsequent escalations cannot be increased by more than approximately 3-fold (a half-log increment). Doses lower than the initial dose of 100 mg may also be administered.

If any of the following scenarios occur, dosing at the current level and further dose escalation will be discontinued:

1. a single participant experiences a SAE or clinically significant event that is related to LY3526318 administration, or
2. if >3 participants at 1 dose level experience moderate treatment-related AEs that impair normal activities.

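### The 154 µg·h/mL exposure ceiling is AUC0-24 in the protocol synopsis but AUC0-inf in Section 4.1, Table 4.1 and SAP 6.0, so the same data can pass one and fail the other

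*Protocol*

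**What the plan says.** The limit of 154 µg·h/mL comes from a 1-month monkey study. It appears with different human metrics:

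- **Protocol 1.1 (Synopsis, Part A):** "Doses will be selected to maintain geometric mean AUC_{0-24} below the lowest NOAEL from animal-toxicology studies".
- **Protocol 4.1:** "these doses would be selected to maintain human $AUC_{0-\infty}$ below the lowest animal-toxicology NOAEL". No type of mean is named.
- **SAP 6.0:** "Doses will be selected to maintain geometric mean $AUC_{0-\infty}$ below the lowest no-observed-adverse-effect level". This nearly repeats the synopsis sentence with a different AUC, yet SAP 7.1 reports no changes from the protocol.
- **Protocol 4.3, Table 4.1, footnote a:** "AUC for humans is AUC_{0-inf} after a single dose".
- **Protocol 4.3, text:** "The determinant of the maximum dose will be the NOAEL AUC of 154". The human limit is called a mean AUC, with no time interval and no type of mean.
- **Protocol 6.6.1:** data are evaluated "until the mean LY3526318 exposure is projected to reach the NOAEL". Again neither the interval nor the type of mean is given.

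For the monkey figure itself, Section 4.3 says "the mean AUC₀₋₂₄ was 154", and footnote a of Table 4.1 calls the animal values AUC over a dosing interval after multiple doses. On data for the decision, the synopsis asks for available PK through 24 hours, and Section 6.6.1 for PK through at least 24 hours.

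**The concern.** A ceiling that fixes the maximum dose must be one quantity. Here it is two, and they differ by whatever exposure falls after 24 hours. Each label has some basis. The animal value is a 24-hour AUC, which fits the synopsis. The human value used to derive 275 mg is an AUC0-inf, which fits Section 4.1 and SAP 6.0.

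A team following the synopsis could escalate on results that a team following Section 4.1 would treat as over the limit. Above 275 mg the stakes rise, because Section 4.3 permits higher doses provided a mean AUC of 154 is not exceeded. The remaining bounds are then the step limit of about 3-fold in Section 6.6.1 and the 1000 mg practical cap.

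**Working it through.** **Inputs**

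- AUC0-inf of 56 µg·h/mL at 100 mg in the prior study (Protocol 4.3).
- Ceiling of 154 µg·h/mL and planned maximum of 275 mg (Protocol 4.3).
- Terminal half-life of 9.72 to 13.5 h with the prior formulation (Protocol 2.2).
- 250 mg as the second fasted dose level (SAP 9.2.2).
- Assumptions found in neither document: an absorption rate ka of 0.3 to 2 per hour or, separately, a distribution phase in which half of the AUC declines with a 3 h half-life. Both are used only to show a range.

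**1. The plan's own figure.** 100 mg × 154/56 = 275 mg exactly. The monkey exposure multiples are 154/56 = 2.75 (stated as 2.8) and 154/154 = 1. The 275 mg therefore rests on AUC0-inf.

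**2. Share of AUC0-inf after 24 h.** With k = ln 2 / half-life:

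- Mono-exponential: tail = exp(−24k), which is 0.181 at 9.72 h and 0.292 at 13.5 h.
- First-order absorption: tail = (ka·e^(−24k) − k·e^(−24ka)) / (ka − k).
- Distribution phase: tail = 0.5·exp(−24k) + 0.5·exp(−24·ln 2/3), which is 0.092 and 0.148.

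**3. What the two readings imply.** AUC0-inf at the synopsis limit is 154/(1 − tail). AUC0-24 at the other limit is 154 × (1 − tail); this is also the AUC0-24 at 275 mg under dose proportionality. The first value in each cell is for 9.72 h, the second for 13.5 h.

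| Assumed shape | Share after 24 h | AUC0-inf when AUC0-24 = 154 | Excess over 154 | AUC0-24 when AUC0-inf = 154 |
|---|---|---|---|---|
| Mono-exponential | 18.1%, 29.2% | 187.9, 217.4 | 22%, 41% | 126.2, 109.1 |
| ka 2 per h | 18.7%, 29.9% | 189.5, 219.8 | 23%, 43% | 125.2, 107.9 |
| ka 0.3 per h | 23.7%, 35.2% | 201.8, 237.5 | 31%, 54% | 117.6, 99.8 |
| Distribution phase | 9.2%, 14.8% | 169.7, 180.7 | 10%, 17% | 139.8, 131.2 |

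**4. At the 250 mg in SAP 9.2.2.** Dose-proportional scaling gives AUC0-inf = 56 × 2.5 = 140, which is below 154 on either reading. Let the new formulation raise exposure by a factor g.

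- On AUC0-inf, 154 is reached at g = 154/140 = 1.10.
- On AUC0-24, it is reached at g = 154/(140 × (1 − tail)) = 1.34 to 1.55 (mono-exponential), or 1.21 to 1.29 (distribution phase).

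Between these values the two rules disagree. For example, an AUC0-inf of 65 at 100 mg (g = 65/56 = 1.16) projects to 65 × 2.5 = 162.5 at 250 mg, above 154. The matching mono-exponential AUC0-24 is 162.5 × 0.819 = 133 or 162.5 × 0.708 = 115, below 154.

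**5. Data at the decision.** With a cut at 24 h, the extrapolated part of AUC0-inf is the share in step 2: about 18% to 29% for mono-exponential decline. Table 2 of the SAP requires no more than 20% for a reliable AUC0-inf. With samples to 96 h, exp(−96k) leaves only 0.1% to 0.7%.

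**The case against.** The synopsis is the one place that ties the human limit to AUC0-24. Section 4.1, Table 4.1 and SAP 6.0 all use AUC0-inf, and Protocol 9.5 points to Section 4.1 for interim data access in support of dose selection. This is a fair reading of where the weight of the text lies, but Section 9.5 gives no section precedence over the synopsis. SAP 3.0 says that the SAP supersedes the protocol's statistical considerations and that substantial differences will be identified. The ceiling is a dose-selection rule, and SAP 7.1 identifies no difference.

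The practical reach may also be small. SAP 9.2.2 shows one fasted escalation, to 250 mg, and Protocol 2.3 expects exposure at 100 mg to be similar to or slightly above the prior study. The second dose would be chosen from PK observed with the new formulation, not by scaling the old value. Part B has its own comparator, the AUC0-24 reached in Part A. All of this stands. Even so, a gain just above 1.10 is enough to separate the rules at 250 mg. Section 4.1 allows for a 2-fold gain, and Section 4.3 says "The current formulation could produce exposures up to 2.5 times those of the prior form for any given dose level". The protocol also still permits three fasted levels.

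The size is uncertain: the half-lives belong to the prior formulation, and the absorption and distribution inputs are assumed. This stands too, and is why a range is shown.

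An unspecified mean is vagueness rather than contradiction, and no coefficient of variation is given from which to size it. It is a secondary point.

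Finally, data beyond 24 h will probably be available. Samples run to 96 h, escalations are about 2 weeks apart, and SAP 7.2 plans a PK report after each dose level. That largely answers the worry about extrapolation, although no text requires a decision to wait for the later samples. It does not say which AUC is compared with 154.

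**Conclusion.** The concern holds. The documents give two different human metrics for one dose-limiting threshold, and nothing in them settles which applies. For the same type of mean the conflict runs one way: results can pass on AUC0-24 and fail on AUC0-inf, not the reverse.

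Under mono-exponential decline, any dose level with an AUC0-inf above 154 and below about 188 (half-life 9.72 h) or 217 (13.5 h) passes the synopsis rule and fails Section 4.1 and SAP 6.0. Across all the shapes tried, the upper edge of that band runs from about 170 to 238. These figures assume that the prior formulation's half-lives carry over to the new one. The existence and direction of the gap do not depend on that assumption. Because the threshold limits dose in healthy participants, it should not be left open, even if few decisions turn on it.

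**What to change.** Reconcile Protocol 1.1, 4.1, 4.3 with Table 4.1, 6.6.1 and SAP 6.0 to one AUC interval and one type of mean. The sponsor must decide which metric governs; this review does not propose one. State the PK data window for each escalation decision to match that metric.

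In SAP 7.2, have each interim PK report show AUC0-24, AUC0-inf and the percentage extrapolated. SAP Table 2 already defines both AUCs and the 20% extrapolation limit for Part A. If any dose decision has already been taken, record which limit was applied.

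The cost is a wording amendment to the protocol and SAP, plus a few columns in reports already planned. No new samples or visits are needed.
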